8.1.4.2 Analysis of Secondary Efficacy Endpoints

The null hypothesis for each secondary efficacy endpoint is that there is no difference between the intensified T2T arm and the SOC arm in the ITT analysis; the alternative hypothesis is that there are differences between the two treatment arms. All statistical tests which will be performed for secondary endpoints are only of exploratory nature and no adjustment for multiple comparisons is planned.

Discrete variables will be summarized using count and percentages will be compared between the two treatment arms using Pearson's chi-square. The Fisher's exact test will be applied instead of the chi-square test, if $\geq 25\%$ of the cells in the frequency table have expected counts less than 5.

Continuous efficacy variables will be summarized by common statistics (number of subjects, mean, 95% confidence interval, standard deviation, first quartile, median, third quartile, minimum and maximum) at Baseline, post-baseline Time points and for change from Baseline to the post-baseline Time points. The changes from Baseline to Week 52 in continuous variables will be compared between the treatment arms using an analysis of covariance method adjusting for the corresponding Baseline values and treatment arm as independent factor. Least square mean values (LSMEAN) for the difference of the mean changes between the two treatment arms and corresponding 95% confidence intervals will be determined. This will be done both for the observed and LOCF imputed values. All further details will be specified in the SAP.

8.1.4.3 Other Exploratory Analyses

Other exploratory analyses will be specified in the SAP.

8.1.5 Pharmacokinetic Analyses

No pharmacokinetic investigations are planned.

8.1.6 Safety Analysis

Safety analyses will be carried out using the safety population, which include all subjects who were randomized and received treatment for axSpA after randomization.

Treatment-emergent AEs and serious AEs (SAEs), which include pre- and post-treatment SAEs, will be summarized and reported, while pre-randomization AEs will be only listed.

Treatment-emergent AEs are defined as AEs that begin either on or after the Baseline Visit up to end of the study. All AEs will be coded using the Medical Dictionary for Drug Regulatory Activities (MedDRA®). The number and percent of subjects experiencing treatment emergent AEs will be tabulated by system organ class and preferred term. In addition, a summary of treatment emergent AEs by severity and relationship to study drug will be presented. AEs, which are serious, severe, or life-threatening, and those which lead to premature study discontinuation will be listed and described in detail.

Mean change in vital signs and laboratory variables at each visit as compared to Baseline will be summarized for all subjects in the safety population, and compared between treatment groups using a one way ANOVA. The last evaluation on or before the Baseline Visit will be used as baseline for all analyses. For selected parameters, a listing of all subjects with any laboratory determination meeting Common Toxicity Criteria (CTC) of Grade 3 or higher will be provided. Shift tables for changes from Baseline according to the normal range will also be provided for laboratory variables.

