After randomization subjects are seen at Weeks 2, 4, 6, 8 and afterwards every 4 weeks up to Week 52. Basic treatment will be started with a non-steroidal anti-inflammatory drug (NSAID). Treatment should be intensified (escalated) beginning at Week 4 if the ASDAS is ≥ 2.1 (escalation step 1). Treatment escalation is planned to be initiated at Week 4, if needed and further escalation is planned at Week 8, if needed (escalation step 2). However, if not required at Week 8, treatment can be escalated at every visit thereafter if the ongoing treatment is not sufficiently efficacious and the escalation step 2 has not yet been reached. Treatment escalation steps are as follows:

Methodology (Continued):**T2T Group (Investigational Group) (Continued):**

- Basic treatment (NSAID 1): Treatment will be started with any NSAID and given for 4 weeks at full anti-inflammatory dose. If at Week 2 ASAS 20 response is not achieved, subjects may early escape to Escalation Step 1. If the chosen NSAID cannot be continued due to intolerance, escalation to the next escalation step is possible at any time point. If basic treatment is well tolerated and sufficiently efficacious the subject will be continued on this treatment.
- Escalation step 1 (NSAID 2): Treatment will be changed to a second NSAID if after 4 weeks of treatment the first NSAID is not sufficiently efficacious (ASDAS ≥ 2.1) and/or not tolerated. The second NSAID will be given for 4 weeks. Early escape is possible if after 2 weeks no ASAS 20 response is achieved. In this case treatment can be switched to escalation step 2 after 2 weeks of NSAID 2. If the chosen NSAID cannot be continued due to intolerance, escalation to the next escalation step is possible at any time point. If NSAID 2 treatment is well tolerated and sufficiently efficacious the subject will be continued on this treatment.
- Escalation step 2 (Combination with adalimumab): In case of failure of NSAID 2 (ASDAS ≥ 2.1 after 4 weeks of NSAID 2) the treatment will be intensified by switching to the combination of NSAID and adalimumab 40 mg s.c. every other week (eow). Escalation step 2 can be initiated at Week 4 visit at the earliest if early escape is chosen during Basic Treatment and during NSAID 2.

SOC Group (Reference Group):

After randomization, subjects will receive treatment according to local practice standards. Subjects are seen at Weeks 12, 24, 32, and 52.

Diagnosis and Main Criteria for Inclusion/Exclusion:**Main Inclusion:**

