3.8 Benefits and Risks

There is an unmet medical need for the treatment of axSpA. A T2T paradigm has been proposed but no data are available to support this treatment approach. In this study, a T2T treatment scheme escalating to combination treatment with one NSAID and adalimumab (if needed) is investigated. The utility of TNF blockade with adalimumab in axSpA has been established in randomized controlled trials which demonstrated a safety profile similar to that observed in the extensive clinical and post-marketing experience of adalimumab in a wide range of disease states. The safety profile of adalimumab in this and other approved indications is well established. Adverse events in the categories of autoimmunity, demyelinating disorders, congestive heart failure, gastrointestinal disorders, hematologic events, hepatic events, hypersensitivity, immunosuppression, infections, malignancies, respiratory thoracic and mediastinal disorders, and vascular disorders have been observed with adalimumab therapy. The investigator is referred to the current Investigator's Brochure where additional and more detailed information regarding potential risks and benefits of adalimumab can be found. The potential benefit of the proposed study in axSpA is that it is designed to evaluate the efficacy and safety of an intensified T2T treatment approach to achieve and maintain remission of disease. As axSpA is associated with considerable pain, reduction in health-related quality of life, and work impairment it would be beneficial to know if using an intensified T2T treatment

approach remission of disease may be achieved and better maintained – while at the same time keeping acceptable adverse events rates – as compared to when using SOC.

In a randomized controlled trial comparing tight control of early psoriatic arthritis (TICOPA)^{19,20} with standard care an increased rate of adverse events (AEs) were seen in the tight control arm: eight serious AEs in the tight control arm compared to two in the SOC arm; altogether 622 AEs (in 97% of patients) in the tight control arm versus 249 (in 80% of patients) with SOC.

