Subjects who initially screen-fail for the study may be permitted to re-screen following re-consent. The reason for screen failure will be captured in the appropriate Electronic Case Report Forms (eCRFs). All screening procedures with the possible exceptions noted below will be repeated. The subject must meet all inclusion and none of the exclusion criteria at the time of re-screening in order to qualify for the study. There is no minimum period of time a subject must wait to re-screen for the study; however, a subject should only be re-screened once for this study upon prior agreement with AbbVie Clinical Monitor. Subjects who have screen-failed previously and do not have a reasonable chance of meeting the inclusion/exclusion criteria should not be re-screened. If the subject had completed initial screening evaluation assessments including HLA-B27, Antinuclear Antibody (ANA), Magnetic Resonance Imaging (MRI) or electrocardiogram (ECG), these tests will not need to be repeated during re-screening provided the conditions noted in Section 5.3 are met and no more than 3 months (90 days) have passed for the ECG and no more than 42 days for the MRI. There is no need to redraw the HLA-B27 or ANA if results from the initial screening are available.

Treatment Period:

This period will begin at the Baseline Visit (Day 1) and will end at the Week 52 visit. At the Baseline Visit, subjects who have signed the informed consent and meet the eligibility (all of the inclusion and none of the exclusion) criteria described in Section 5.2.1 and Section 5.2.2 will be enrolled and randomized in a 1:1 ratio to receive either intensified T2T treatment or SOC treatment. Study physician and patients might be aware of the allocated treatment group. However, an influence of the SOC treatment based upon knowledge and potential benefits/risks in the intensified T2T treatment arm is not expected based on experience of other T2T-Studies like TICOPA.²⁰

T2T Group (Investigational Group):

After randomization, subjects are seen at Weeks 2, 4, 6, 8 and afterwards every 4 weeks up to Week 52.

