At Baseline and all subsequent visits, the investigator will document new onset of uveitis and/or the number of flares, including specific eye (right, left or both), since the last visit. The corresponding AE eCRF should also be completed. Initial documentation of uveitis must be confirmed by an ophthalmologist. Flares following initial confirmation by an ophthalmologist can be self-reported by the subject.

Physical Examination

A full physical exam will be performed by medically qualified personnel at the designated study visits in Table 1. Physical examination findings that are related or part of each subject's medical history should be captured on the appropriate eCRF page. The physical exam at the Baseline Visit will serve as the Baseline exam for the entire study.

A symptom-directed physical examination can be performed at any other visits if, in the opinion of the Investigator, it is warranted by the subject's AE status or on review of symptoms. Any clinically significant physical examination findings after the Baseline Visit – or worsening of pre-existing findings – will be recorded as adverse events. For further definition of an adverse event please refer to Section 6.1.1.

12-Lead Electrocardiogram (ECG)

A resting 12-lead ECG will be performed at the Screening Visit. A qualified physician will interpret, determine the clinical significance of any abnormal finding, sign, and date each ECG. Any clinically significant findings will be documented in the source documents and later transcribed on to the appropriate eCRF. If there is no clinically significant finding this needs to be confirmed in the eCRF. Each signed original ECG will be monitored by the responsible Clinical Research Associate (CRA) and kept with subject's source documents onsite.

For subjects with a normal ECG taken within 90 days of Screening, a repeat ECG at Screening will not be required, provided all protocol required documentation is available and nothing has changed in the subject's health status since the time of the test that warrants a repeat test. If there are other findings that are clinically significant, the Principal Investigator must contact the Study Designated Physician before enrolling the subject.

Subjects can have a repeat ECG at any time during the study as warranted based on the opinion of the Investigator.

Chest X-Ray (CXR)

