6.1 Medical Complaints

The Investigator will monitor each subject for clinical and laboratory evidence of adverse events on a routine basis throughout the study. The Investigator will assess and record any adverse event in detail including the date of onset, event diagnosis (if known) or sign/symptom, severity, time course (end date, ongoing, intermittent), relationship of the adverse event to Humira, and any action(s) taken. For serious adverse events considered as having "no reasonable possibility" of being associated with Humira, the Investigator will provide an "Other" cause of the event. For adverse events to be considered intermittent, the events must be of similar nature and severity. Adverse events, whether in response to a query, observed by site personnel, or reported spontaneously by the subject will be recorded.

All adverse events will be followed to a satisfactory conclusion.

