6.1.4 Adverse Event Collection Period

All adverse events reported from Baseline until 70 days following discontinuation of study drug administration have elapsed will be collected, whether solicited or spontaneously reported by the subject. In addition, serious adverse events and protocol-related nonserious adverse events will be collected from the time the subject signed the study-specific informed consent. Adverse event information will be collected and recorded on the appropriate eCRFs.

Subjects who continue on Humira therapy eow after the end of study participation will not be contacted for follow-up as any new adverse events should be reported through the mechanism used for all post-marketing adverse experiences. All other subjects of the T2T group treated with study drug will be contacted approximately 70 days following study drug discontinuation for an assessment of any new or ongoing AEs. The 70-day follow-up call will not be required for subjects of the SOC group. The end-of-study is defined as the date of the last subject's last visit or the actual date of follow-up contact, whichever is later. All SAEs and all ongoing adverse events reported during the 70-day follow-up phone call must be captured in the clinical database.

Figure 2. Adverse Event Collection

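### Non-serious AEs are asked about at 15 post-baseline visits in T2T but 4 in SOC, so the crude AE percentages in 8.1.6 are not comparable between arms, by an amount the protocol cannot fix

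*Protocol*

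**What the plan says.** For T2T, Section 5.1 states: "After randomization, subjects are seen at Weeks 2, 4, 6, 8 and afterwards every 4 weeks up to Week 52". For SOC, the Synopsis states: "Subjects are seen at Weeks 12, 24, 32, and 52". In both schedules of Table 1 AE monitoring is tied to the visits, and no SOC contact between visits is planned.

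Section 6.1 defines how AEs reach the database: "Adverse events, whether in response to a query, observed by site personnel, or reported spontaneously by the subject will be recorded". Section 5.3.1.1 adds a route through examinations: "Any clinically significant physical examination findings after the Baseline Visit" are to be recorded as AEs. For uveitis, the same section has the investigator document flares since the last visit and complete an AE form.

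Section 8.1.6 summarises the result as follows: "The number and percent of subjects experiencing treatment emergent AEs will be tabulated by system organ class and preferred term". It adds summaries by severity and relationship, and a listing and description of AEs that are serious, severe, life-threatening or lead to premature discontinuation. It specifies no between-arm test for AEs and no common look-back.

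Section 3.8 frames the benefit-risk question as whether remission can be reached while AE rates stay acceptable compared with SOC. It then reports, for a strategy trial in psoriatic arthritis, "altogether 622 AEs (in 97% of patients) in the tight control arm versus 249 (in 80% of patients) with SOC".

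**The concern.** Two of the three capture routes, querying and site observation, work mainly when the subject is at the site. The third, spontaneous report, works at any time. A cold or a few days of dyspepsia is more likely to be reported when the question comes within 4 weeks than when it comes up to 20 weeks later. So even if the two strategies caused exactly the same events, the T2T column of the AE table would tend to be fuller.

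What is at stake is the reading of that table. The strategy's tolerability relative to SOC is part of the stated benefit-risk question, and Section 3.8 shows how crude percentages and counts from two arms get read side by side. A difference in how often subjects were asked could be taken for harm of the strategy. This is separate from the 70-day follow-up call, which SOC does not have (Section 6.1.4: "The 70-day follow-up call will not be required for subjects of the SOC group") and which adds observation after Week 52.

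**Working it through.** The protocol gives no figure for AE capture or recall, so there is nothing of its own to reproduce. The check has two parts: what the schedule fixes, and what it could do under declared assumptions.

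**Schedule (Section 5.1, Synopsis, Table 1).**
- T2T: Weeks 2, 4, 6, 8, 12, 16, ..., 52. That is 15 visits, with gaps of 4 × 2 weeks and 11 × 4 weeks (8 + 44 = 52). The T2T row of Table 1 is misaligned in the text at hand; it is read here as marked at every visit.
- SOC: Weeks 12, 24, 32, 52. That is 4 visits, with gaps of 12, 12, 8 and 20 weeks (sum 52).
- Mean time from an event to the next visit, if events fall evenly over time, is Σ(gap²/2)/52. T2T: (4×4 + 11×16)/(2×52) = 192/104 = 1.8 weeks. SOC: (144 + 144 + 64 + 400)/(2×52) = 752/104 = 7.2 weeks.

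**Recall model (assumptions, not in the protocol).** AEs arise at the same constant rate in both arms. An AE that occurred t weeks before the next visit is reported with probability 2^(−t/h), where h is a recall half-life. With k = ln2/h:

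captured share c = Σ[(1 − e^(−k·gap))/k] / 52

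For h = 4, k = 0.1733:
- T2T: 4 × 1.690 + 11 × 2.885 = 38.50; 38.50/52 = 0.740.
- SOC: 2 × 5.049 + 4.328 + 5.590 = 20.02; 20.02/52 = 0.385.

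For a term with true 52-week incidence p, the observed percentage is 1 − (1 − p)^c. With p = 20% and h = 4: T2T 1 − 0.8^0.740 = 15.2%; SOC 1 − 0.8^0.385 = 8.2%.

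| h (weeks) | Share T2T | Share SOC | Ratio | Observed, true 20% (T2T vs SOC) | Difference (points) |
|---|---|---|---|---|---|
| 4 | 0.740 | 0.385 | 1.92 | 15.2% vs 8.2% | 7.0 |
| 8 | 0.856 | 0.581 | 1.47 | 17.4% vs 12.2% | 5.2 |
| 12 | 0.901 | 0.684 | 1.32 | 18.2% vs 14.2% | 4.1 |
| 26 | 0.952 | 0.832 | 1.15 | 19.1% vs 16.9% | 2.2 |
| 52 | 0.976 | 0.910 | 1.07 | 19.6% vs 18.4% | 1.2 |

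Differences are taken before rounding.

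**If half of all AEs are never forgotten**, c becomes 0.5 + 0.5c. At h = 4 that is 0.870 vs 0.692, and a true 20% is observed as 1 − 0.8^0.870 = 17.6% vs 1 − 0.8^0.692 = 14.3%, about 3.3 points. For a true 50% incidence the same assumption gives 45.3% vs 38.1% (h = 4) and 49.2% vs 47.0% (h = 26).

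In this model the difference never favours T2T and vanishes only with perfect recall. Dividing by person-time would not remove it, because the 52 weeks are common to both arms.

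**The case against.** The other side has real weight.

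- **The AE table is descriptive.** Section 8.1.6 specifies no AE test, and Section 4.0 lists no safety objective. This stands: the risk is one of reading, not of a false test result. Section 3.8 nevertheless invites the comparison with SOC.
- **The table is not a single figure per arm.** A reader might infer that safety is reduced to one crude percentage. The percentages are by system organ class and preferred term, with severity and relationship summaries, and the weightier events are described separately.
- **Details belong to the SAP.** Section 8.1.2 defers them there, and a supplementary table could well sit in a plan not shown. But the unequal enquiry is fixed by Table 1 and the crude summary by 8.1.6. No later analysis can recover events that were never recorded.
- **The size is assumed.** The protocol gives no half-life. Spontaneous reports are recorded too, and nothing shows that SOC patients do not see their physician between study visits. This stands, and it rules out quoting any single figure.
- **The cited psoriatic arthritis trial.** A reader might take its 622 vs 249 AEs as proof of the artefact. The protocol gives neither that trial's visit schedule nor a cause, and SAEs also differed (8 vs 2), so the figures do not show it.
- **An equal-look-back table has its own bias.** If an examination or laboratory finding is dated at detection, a 28-day window in SOC collects abnormalities accumulated over 8 to 20 weeks, against about 4 in T2T. The ±7-day visit window (Section 5.3.1) lets a nominal 4-week gap run from 2 to 6 weeks, and TB prophylaxis can postpone T2T visits. This stands, and it is why such a table cannot carry the safety comparison.

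**Conclusion.** The concern holds in limited form. Within the common 52 weeks, AE enquiry is fixed at 15 visits against 4, and 8.1.6 puts the resulting crude percentages side by side without a caution. Non-serious, mild and short AEs are likely to be under-recorded in SOC relative to T2T. SAEs, AEs leading to discontinuation and spontaneously reported AEs should be little affected.

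The direction follows from the schedule; the size does not. Under equal true rates and exponential recall loss with a half-life of 4 to 52 weeks, the artefact for a true 20% term runs from about 7 points to about 1, and is smaller if many AEs are never forgotten. A reader might go further and conclude that recall loss will make T2T look less safe by a known amount, or that any T2T excess is an artefact. The protocol supports neither: a real excess from the strategy remains possible, and the two cannot be separated in the full table. The primary endpoint is not touched.

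**What to change.** Amend Section 8.1.6, leaving the visit schedule as it is:

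1. Keep the full treatment-emergent AE table as a description of each arm, and state that unequal visit frequency limits between-arm reading of non-serious AEs.
2. Base between-arm safety statements mainly on SAEs, severe AEs and AEs leading to discontinuation, tabulated by arm over the common 52 weeks.
3. Add a supplementary sensitivity table, in both arms, of subject-reported (symptomatic) AEs with onset in the 28 days before the actual dates of the Week 12, 24, 32 and 52 visits. The preceding T2T visits are Weeks 8, 20, 28 and 48, each nominally 4 weeks earlier. Exclude findings dated only by their detection at an examination or laboratory test.

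The cost is a few sentences and some extra tables, built from the AE onset dates that Section 6.1 already requires. The downsides should be stated with the table. It covers about 4 × 4 = 16 of 52 weeks, so it is less precise. It omits Weeks 0 to 8, when NSAID switches occur and adalimumab can first start (Week 4). It equalises the look-back only approximately, because of the ±7-day windows and postponed T2T visits.

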Mean change in vital signs and laboratory variables at each visit as compared to Baseline will be summarized for all treated subjects, and compared between treatment groups using a one way Analysis of Variance (ANOVA). The last evaluation on or prior to the Baseline visit will be used as baseline for all analyses. For selected parameters, a listing of all subjects with any laboratory determination meeting Common Toxicity Criteria (CTC) of Grade 3 or higher will be provided. Shift tables for changes from Baseline according to the normal range will also be provided for laboratory variables.

Sample Size:

Based on available data from previous studies it is assumed that ASDAS inactive disease could be reached by 40% in the T2T group versus 20% in the control group. In total 2×90 evaluable subjects are necessary to detect with 80% power an increase in ASDAS inactive disease at Week 32 from 20% in the SOC arm to 40% in the intensified T2T arm, if a two sided Fisher's exact test is applied. If the Pearson chi-square test instead of the Fisher's exact test can be applied (see Section 8.1.4.1), then only 2×83 subjects are necessary.

Assuming that about 18% of the randomized subjects will drop out prior to Week 32 and have to be counted as non-responder the assumed ASDAS inactive disease rate will be diluted to 16.4% in the SOC arm and 32.8% in the intensified T2T arm. The necessary sample size for this scenario (intent to treat [ITT] population) is 2×109 subjects for the chi-square test and 2×119 subjects for the Fisher's exact test. In summary, 2×120 subjects should be randomized.

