For any subject with clinical signs/symptoms of active TB or newly identified TB risk factors a CXR may be required for evaluation of active TB and the site should contact the AbbVie Medical Monitor for further discussion. Subjects with confirmed active TB should be discontinued from the study and receive standard of care treatment for TB.

Pregnancy Tests

A serum pregnancy test will be performed at the Screening Visit on all female subjects of childbearing potential. At the Baseline Visit, subjects of childbearing potential will have

a urine pregnancy test performed locally by designated study personnel. If any urine pregnancy test is positive, a serum pregnancy test will be performed. A lactating or pregnant female will not be eligible for participation or continuation in this study.

All women of childbearing potential will have a repeat urine pregnancy test at the final study visit performed locally by designated study personnel.

Females of non-childbearing potential (either postmenopausal or permanently surgically sterile as defined above) at Screening do not require pregnancy testing.

Laboratory Analyses

Blood and urine samples will be obtained for clinical laboratory tests. Samples will be obtained at the designated study visits in Table 1. Samples will be obtained for the laboratory tests listed in Table 2.

The local laboratory of the respective study site will be utilized to process and provide results for the clinical laboratory tests, except for autoantibodies against CD74 CLIP. The local laboratory will provide instructions regarding the collection, processing and shipment of appropriate samples.

The laboratory results will be provided by the local laboratory to the investigative site where they will be reviewed, signed and dated by the Investigator and filed as source data. For any abnormal value outside of the reference range, the Investigator will indicate on the report if the result is clinically significant (CS) or not clinically significant (NCS). All abnormal laboratory test results that are considered clinically significant by the Investigator will be followed to a satisfactory resolution.

A certified central laboratory will be utilized to process and provide results for the testing of autoantibodies against CD74 CLIP. The central laboratory chosen for this study will provide instructions regarding the collection, processing and shipment of appropriate samples.

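### Laboratory and vital-sign changes are compared between arms by one-way ANOVA without the baseline value as covariate, which gives up some precision at no saving

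*Protocol*

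**What the plan says.** Protocol Section 8.1.6 takes as its outcome "Mean change in vital signs and laboratory variables at each visit as compared to Baseline". These changes are to be summarised for the safety population and "compared between treatment groups using a one way ANOVA". The Synopsis (Section 1.2, Statistical Methods, Safety) names the same method. Neither place mentions a covariate.

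The same section defines the baseline value: "The last evaluation on or before the Baseline Visit will be used as baseline for all analyses".

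For continuous efficacy variables, Section 8.1.4.2 compares changes to Week 52 "using an analysis of covariance method adjusting for the corresponding Baseline values".

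On timing, Section 5.1 says of the T2T arm: "After randomization, subjects are seen at Weeks 2, 4, 6, 8 and afterwards every 4 weeks up to Week 52". For the standard-of-care (SOC) arm the Synopsis says: "Subjects are seen at Weeks 12, 24, 32, and 52". Section 5.3.1.1 ties laboratory sampling to that schedule: "Samples will be obtained at the designated study visits in Table 1". After Baseline, the SOC part of Table 1 has only those four visits and the Discontinuation Visit.

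**The concern.** A one-way ANOVA has one factor, the arm. Applied to a change score, it fixes the weight on the baseline value at exactly one. When baseline and follow-up are imperfectly correlated, that weight is too large: part of the baseline noise is carried into the change and widens the standard error of the arm difference. ANCOVA estimates the weight from the data. The protocol already uses that approach for efficacy, defines the baseline value it would need for safety, and gives no reason for treating the two differently.

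What is at stake is precision in the between-arm differences in liver enzymes, creatinine, blood counts and blood pressure. The sample size was set by the primary efficacy endpoint, so precision for these comparisons is whatever the collected data can give.

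A second, smaller matter is that the comparison is worded for each visit, while the two arms have different visit schedules.

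**Working it through.** The plan gives no figure for the precision of this comparison, so there is none to reproduce. The check has two parts.

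**1. Precision of the two models**

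Inputs:
- Outcome: change from Baseline; model with arm only (Section 8.1.6).
- Alternative: the same change with the baseline value added (the method of Section 8.1.4.2).
- Planned size: 120 per arm (Section 8.2).
- Correlation r between baseline and follow-up within arm: not in the documents, so assumed over 0.3 to 0.9.
- Variance s² equal at baseline and follow-up: also an assumption.

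Variance per subject that enters the arm difference:
- ANOVA on change: s² + s² − 2rs² = 2s²(1 − r)
- ANCOVA: s²(1 − r²) = s²(1 − r)(1 + r)
- Ratio, ANCOVA to ANOVA: (1 + r)/2

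| Assumed r | Variance ratio (1 + r)/2 | Fall in standard error, 1 − √ratio | Equivalent gain in sample size, 1/ratio |
|---|---|---|---|
| 0.3 | 0.65 | 19% | 1.54 times |
| 0.5 | 0.75 | 13% | 1.33 times |
| 0.7 | 0.85 | 8% | 1.18 times |
| 0.9 | 0.95 | 3% | 1.05 times |

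A simulation with 120 per arm and 4,000 repetitions gave variance ratios of 0.751 at r = 0.5 and 0.846 at r = 0.7, against 0.75 and 0.85 from the formula.

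The equal-variance assumption affects the size of the gain, not its direction. With standard deviations a at baseline and b at follow-up, the ANOVA variance minus the ANCOVA variance is (a² + b² − 2rab) − b²(1 − r²) = (a − rb)², which is never negative. The price of the covariate is one degree of freedom: 240 − 2 = 238 becomes 237 with all subjects contributing.

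**2. Visits at which both arms have data**

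- T2T: Weeks 2, 4, 6 and 8 (4 visits), then every 4 weeks from Week 12 to Week 52, (52 − 12)/4 + 1 = 11 visits; total 15.
- SOC: Weeks 12, 24, 32 and 52; total 4, all shared with T2T.
- T2T only: 15 − 4 = 11 visits, namely Weeks 2, 4, 6, 8, 16, 20, 28, 36, 40, 44 and 48.

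At those 11 visits there is no scheduled SOC value, so no arm contrast can be formed. Section 8.1.6 does not say so.

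**The case against.** The strongest case on the other side is that no error has been shown. Under 1:1 randomization, ANOVA on change is valid and unbiased, and using a simpler model for supportive safety summaries than for efficacy is a choice, not a contradiction. That stands. What remains is that the choice gives up precision and saves nothing.

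It can also be said that Section 8.1.2 leaves analysis detail to the statistical analysis plan. For the list of visits that is a fair answer. It is weaker for the model, because the protocol names the model itself, in two places.

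The size of the gain is open to challenge too. It rests on an r that the documents do not give. Body weight is among the vital signs in Section 5.3.1.1 and may well be highly correlated over time; at r = 0.9 the standard error falls by only 3%.

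A reader might infer three stronger things that the documents do not support:

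- **That baseline is ignored, or that the result is biased through regression to the mean.** Baseline is subtracted in forming the change. A chance imbalance between randomized arms is random error, already reflected in the standard error.
- **That the analysis fails at 11 visits.** The summaries can be produced at every visit. A comparison at a visit with one arm gives no result; it does not give a wrong one. This is a matter of wording.
- **That the trial's safety conclusion is undermined.** No safety hypothesis, margin or power is stated. Section 3.8 frames the safety question as adverse-event rates, and Section 8.1.6 also provides adverse-event tables, listings of Grade 3 or higher laboratory values and shift tables. None of these depends on the choice between ANOVA and ANCOVA.

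**Conclusion.** The point holds as a minor efficiency improvement. The protocol fixes a valid but less precise model for between-arm comparison of laboratory and vital-sign changes, although the covariate that would sharpen it is collected and defined. Given equal variances at baseline and follow-up, the variance of the arm difference would fall to between 0.65 and 0.95 of its value for r from 0.3 to 0.9. The lower end of that gain is close to negligible and the upper end is worth having. Where each parameter lies in the range cannot be settled from the documents.

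The count of 11 T2T-only visits needs no assumption, but it calls only for a clarification. These comparisons are supportive, and neither the primary analysis nor the sample size is touched.

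**What to change.** In Section 8.1.6 and in the Synopsis, replace one-way ANOVA with ANCOVA on the change from Baseline, with arm as factor and the subject's baseline value of the same parameter as covariate, reporting the adjusted arm difference with its 95% confidence interval.

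In the same sentence, state that the arms are compared at Weeks 12, 24, 32 and 52, and that the other 11 T2T visits are summarised descriptively for that arm.

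The cost is a wording change in two places and one covariate in the program. No further data, visits or subjects are needed.
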